### Serious Adverse Events

A Serious Adverse Event (SAE) is any AE occurring during the study that results in any of the following outcomes:

- Death.
- A life-threatening AE that placed the subject, in the view of the Investigator, at immediate risk of death.
- Inpatient hospitalisation or prolongation of existing hospitalisation.
- A persistent or significant disability/incapacity.
- A congenital anomaly/birth defect.
- Important medical event that may require medical or surgical intervention to prevent one of the above outcomes.

In the present study, inpatient hospitalisation for the treatment of PCa will not be considered an SAE, unless the hospitalisation is considered by the Investigator to be causally related to IMP administration or other study procedures or is prolonged compared with what would be anticipated in that subject, i.e. not in agreement with the patient's scheduled treatment protocol. Likewise, other planned procedures already known and anticipated at the time of enrolment will not be considered SAEs unless similarly complicated or prolonged.

An important medical event that may not result in death, be life-threatening, or require hospitalisation may be considered an SAE when, based upon appropriate medical judgment, it may jeopardise the subject and may require medical or surgical intervention to prevent one of the outcomes listed in this SAE definition.

Minimum criteria for SAE reporting are: The event or outcome meets the SAE definition, the event happens to an identifiable subject, and the event is reported by an identifiable and qualified reporter (usually an Investigator or other qualified study centre personnel).

SAEs must be reported within 24 hours of the Investigator or study staff becoming aware of an SAE, regardless of the time that may have elapsed since the time the event occurred and regardless of the causal relationship of IMP to the event. An initial SAE report will be submitted by the Investigator to the pharmacovigilance (PV) provider, and follow-up reports will be provided later as needed. Follow-up reports to an SAE should be prepared when any relevant changes in the condition of the study subject occur after the initial report or if any new relevant information on the SAE becomes available. SAEs should be followed up until resolved or until the event is considered chronic and/or stable outcome.

The PV provider in this study is PharSafer Associates Ltd. The contact information for SAE reporting is located in the ISF.

### Suspected Unexpected Serious Adverse Reactions

An unexpected adverse drug reaction is any serious adverse drug reaction (ADR), the nature or severity of which is not consistent with the approved Reference Safety Information contained within the current Investigator's Brochure (IB) of F-rhPSMA-7.3. Suspected unexpected serious ADRs (SUSARs) are subject to expedited reporting to the CA. The PV provider reports all authority-reportable AEs to the Sponsor and the CA.

## 7.4 Assessment of pharmacokinetics

### 7.4.1 Blood sampling

Blood samples for  $^{18}\text{F}$  radioactivity counting and % radioactive parent/metabolite analysis will be taken from peripheral venous blood.

#### Healthy Volunteers

Blood samples should be collected at the following time-points as calculated from the time of  $^{18}\text{F}$ -rhPSMA-7.3 administration: 30 sec, 60 sec, 90 sec, 4 min 30 sec, 5 min, 6 min, 7 min, 8 min, 15 min, 31 min, 47 min, 75 min, 120 min, 180 min, and 250 min after injection. Sample volume is 2 ml except at the 5, 8, 15, 31, and 47 min time points when an extra 5 ml sample is collected for radioactive metabolite analysis.

#### PCa Patients

Blood samples should be taken at the following time points as calculated from the time of  $^{18}\text{F}$ -rhPSMA-7.3 administration: 20 sec, 40 sec, 60 sec, 80 sec, 100 sec, 120 sec, 140 sec, 160 sec, 180 sec, 4 min, 5 min, 7.5 min, 10 min, 15 min, 20 min, 30 min, 40 min, 50 min, 59 min, and 120 min after the injection. Sample volume is 2 ml except at the 5, 10, 20, 30, 40, and 50 min time points when an extra 5 ml sample is collected for radioactive metabolite analysis.

### 7.4.2 Urine sampling

Urine samples should be collected in timed fractions before the tracer injection, during the scanning break(s) and after the scan. Urine samples should be collected in the following fractions as calculated from the time of  $^{18}\text{F}$ -rhPSMA-7.3 administration: until -5 min, -5 to 95 min, 95 to 185 min and 185 to 255 min (healthy volunteers) or until -5 min, -5 to 50 min, 50 to 125 min and 125 to 240 min (patients with PCa). The collection times are approximations and will depend on actual voiding times.

### 7.4.3 Sample analyses

Radioactivity measurements will be performed for blood and urine samples collected from the study subjects after IMP administration. The analytics will be performed according to standard practises of TPC.

### 7.4.4 Pharmacokinetic parameters

- Metabolite-corrected tracer  $\text{AUC}(0-\text{t}_{\text{last}})$ ,  $\text{C}_{\text{max}}$  and  $\text{t}_{\text{max}}$  of total  $^{18}\text{F}$ -radioactivity in whole blood and plasma
- Total  $^{18}\text{F}$ -radioactivity in urine
- Fractions (%) of radioactive compounds (parent and metabolites) in plasma.

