## 2.4 Secondary endpoints

The secondary endpoints of the study are:

1. Dosimetry estimates and cumulated activity exposure by source region and the entire body including analysis of activity in whole blood, plasma and excreted urine in healthy volunteers.
2. Uptake of  $^{18}\text{F}$ -rhPSMA-7.3 injection visualised by PET imaging compared to histopathology in subjects with PCa, if histopathology information is available.
3. Use of kinetic modelling data to investigate distribution of  $^{18}\text{F}$ -rhPSMA-7.3 in subjects with PCa.
4. Use of kinetic modelling data to optimise the imaging protocol for future studies in subjects with PCa, by estimating *in vivo*  $^{18}\text{F}$  radioactivity in PCa lesions.
5. Analysis of % of radioactive parent compound present in plasma over time in healthy volunteers and subjects with PCa. Relative proportions of radioactive tracer metabolites will be monitored, as well, if detected in significant amounts in the radio-HPLC analysis.

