### 7.2.2 Uptake irreversibility/reversibility

Kinetics of F-rhPSMA-7.3 uptake in PCa lesions is compared to the availability of parent F-rhPSMA-7.3 in plasma by plotting SUVR of lesion and parent F-rhPSMA-7.3 in plasma, and by irreversible and reversible multiple-time graphical analyses (Patlak and Logan plots) (Logan, 2000).

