## 8.2.9 Analysis of pharmacokinetic variables

F radioactivity concentrations will be determined in whole blood, plasma and urine. The concentrations will be presented using descriptive summary statistics. Time-activity curves will be generated and summarised.

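### Does the first bullet of protocol section 7.4.4 define parent tracer and total radioactivity as a single quantity?

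*Protocol*

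**What the plan says.** The first bullet of section 7.4.4 begins with "Metabolite-corrected tracer", names AUC from 0 to tlast, Cmax and tmax, and ends with total 18F "radioactivity in whole blood and plasma". The last bullet of the same section lists "Fractions (%) of radioactive compounds (parent and metabolites) in plasma".

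Other sections bear on the matrix and the timing:

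- Section 2.4, endpoint 5: "Analysis of % of radioactive parent compound present in plasma over time in healthy volunteers and subjects with PCa".
- Section 7.2.2 compares lesion uptake with parent tracer "in plasma by plotting SUVR of lesion and parent".
- Section 8.2.9: 18F "radioactivity concentrations will be determined in whole blood, plasma and urine". It adds time-activity curves and names neither AUC nor metabolite correction.
- Section 7.4.1, volunteers: 2 ml samples "except at the 5, 8, 15, 31, and 47 min time points when an extra 5 ml sample is collected" for metabolite analysis.
- Section 7.4.1, patients: 2 ml samples "except at the 5, 10, 20, 30, 40, and 50 min time points when an extra 5 ml sample is collected" for the same purpose.

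Section 8.2.1 leaves detailed analysis information to a separate SAP, which is not at hand. Section 8.2.2 states that there are no formal hypotheses.

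**The concern.** Metabolite-corrected activity is the parent compound alone. Total activity is parent plus radiolabelled metabolites. One value cannot be both, so the bullet read as a single phrase contradicts itself. It would also ask for a corrected value in whole blood, although the parent fraction is listed for plasma.

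The sampling schedule adds to the doubt. Parent fractions are measured over a much shorter window than total activity, so a parent AUC carried to the last radioactivity sample would rest largely on extrapolation. Apart from the abbreviation list, AUC, Cmax and tmax appear only in section 7.4.4, so no other section states the intended reading outright. At stake is whether a reader of the report would know which quantity an AUC describes, in which matrix, and up to what time.

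**Working it through.** The protocol states no AUC, so there is no figure to reproduce. The check sets the sampling schedule against the possible readings.

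**1. Sampling windows** (section 7.4.1; footnote e of Tables 2 and 3 agrees)

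| | Volunteers | Patients |
|---|---|---|
| Radioactivity samples | 15, from 30 sec to 250 min | 20, from 20 sec to 120 min |
| Parent-fraction samples | 5, from 5 to 47 min | 6, from 5 to 50 min |
| Radioactivity samples before 5 min | 4 | 10 |
| Radioactivity samples after the last parent sample | 4 (75, 120, 180, 250 min) | 2 (59, 120 min) |

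Time without parent data at the end:

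- volunteers: 250 − 47 = 203 min, and 203/250 = 81 %;
- patients: 120 − 50 = 70 min, and 70/120 = 58 %.

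These are shares of clock time, not of AUC. They matter only if someone carries a corrected AUC to the last radioactivity sample, and no section asks for that.

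**2. Which reading fits**

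- *One phrase:* a metabolite-corrected value of total activity in two matrices. This contradicts itself.
- *A list:* AUC of metabolite-corrected tracer, then Cmax and tmax of total activity in whole blood and plasma. This fits the schedule. No parent fraction is measured before 5 min, so in those first minutes Cmax and tmax can be observed directly only for total activity. In patients, parent sampling to 50 min covers the 45-min dynamic scan of section 6.2, which is where parent in plasma is used (section 7.2.2).

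**3. What the list reading leaves open**

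- *Matrix of the parent AUC.* Endpoint 5, section 7.2.2 and the last bullet of 7.4.4 all give plasma. Section 8.2.4 and the synopsis speak of parent in blood or blood samples. That is most likely the specimen drawn, since section 7.4.1 also describes blood samples taken for parent analysis.
- *End time.* By ordinary usage tlast is the last measurable sample of the quantity being integrated: 47 or 50 min for parent, 250 or 120 min for total activity. The protocol does not say that one tlast serves both.
- *AUC of total activity.* None is listed on this reading, and no other section promises one.

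**4. Size**

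No plasma curve or parent fraction is given, so any size rests on assumption. As an illustration, take a curve 0.8·exp(−ln2·t/3) + 0.2·exp(−ln2·t/120), with t in minutes. Let the parent fraction fall exponentially from 1 to 0.8 at the last parent sample, and apply the trapezoid rule at the protocol's times.

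| Ratio | Volunteers | Patients |
|---|---|---|
| Parent AUC to last parent sample / total AUC to last radioactivity sample | 0.36 | 0.54 |
| Total AUC to last parent sample / total AUC to last radioactivity sample | 0.39 | 0.58 |
| Parent / total over the same window | 0.36/0.39 = 0.92 | 0.54/0.58 = 0.93 |

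Most of the gap therefore comes from the window, and little from parent versus total. With slow half-lives of 60 to 240 min and end fractions of 0.95 to 0.6, the first ratio runs from 0.26 to 0.53 in volunteers and from 0.45 to 0.65 in patients. The spread follows the assumptions and says nothing about this tracer.

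**The case for a change.** The case for an edit is that the text is unclear as printed and the remedy costs nothing. Even the list reading leaves the parent AUC without a matrix in its own bullet and gives no AUC of total activity. A SAP can add integration rules, but it must either depart from this wording or repeat it. Section 8.2.4 plans geometric means and CVs for PK assessments, so values will be tabulated under the definition. Splitting the bullet would need no new sample.

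It stands that the bullet is loosely worded and that separate lines for parent and total activity would read better. The rest is weaker. The matrix follows from three other places. Integration limits and the handling of the parent fraction outside its sampled window are details a protocol commonly leaves to the SAP. The long extrapolation arises only if a single tlast is imposed, which the protocol does not do. Report tables carry their own labels for quantity, matrix and time span, so it does not follow that a reader would be left guessing. Extra metabolite aliquots at later draws would add blood volume and HPLC runs without serving any stated objective.

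**Conclusion.** This is a clerical looseness that analysts would resolve as a matter of course, and the plan need not change. The sampling counts are right and the two quantities are indeed run together. A workable reading exists, however, and the schedule supports it. Whichever reading is taken, the same samples are drawn and the same concentrations and parent fractions are measured.

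The consequence is confined to the labelling of descriptive pharmacokinetic summaries. AUC, Cmax and tmax are not among the five secondary endpoints of section 2.4, and no hypothesis or stated decision depends on them. The primary safety endpoint, the image-based dosimetry and the kinetic analysis of the 45-min dynamic scan are untouched.

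This rests on two assumptions: that tlast is taken separately for each quantity, as is usual, and that the reported tables name the quantity and matrix. The SAP could not be consulted on either. The effect on an AUC value cannot be determined from the protocol.

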## 8 STATISTICS AND DATA MANAGEMENT

### 8.1 Estimation of sample size

Sufficient numbers of evaluable subjects have been planned to be included in the study in order to fulfil the study objectives, at the same time limiting the groups of healthy volunteer and patient volunteer subjects to the smallest informative numbers.

Altogether 15 evaluable subjects will be included in the study: 6 evaluable healthy volunteer subjects (3 males, 3 females) and 9 evaluable subjects with PCa (3 in each patient cohort). A patient is considered evaluable if at least one positive lesion on the F-rhPSMA-7.3 scan is seen (see Section 4.10).

### 8.2 Statistical methods

A summary of the statistical methods is given below.

#### 8.2.1 Statistical Analysis Plan

Detailed statistical analysis information will be provided in a separate Statistical Analysis Plan (SAP), to be approved and signed before the database lock.

#### 8.2.2 Statistical hypotheses

No formal statistical hypotheses are stated. This study is exploratory in nature.

#### 8.2.3 Data sets to be analyzed

The safety analysis set (SAF) will include all subjects who received any administration of the IMP.

Evaluable Analysis set (EAS) will include subjects who met all inclusion and exclusion criteria, received IMP, underwent PET/CT scans and met the scan evaluability criteria set out in section 4.10.

Statistical analyses for the primary and secondary endpoints (besides safety) will be performed using EAS. Safety will be assessed using the safety analysis set (SAF).

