### 2.2 Secondary objectives

The secondary objectives of the study are:

1. To determine the biodistribution of  $^{18}\text{F}$  following i.v administration of  $^{18}\text{F}$ -rhPSMA-7.3 and hence calculate the internal radiation dosimetry and the effective dose (ED) in healthy volunteers.
2. To explore the optimisation of PET imaging with  $^{18}\text{F}$ -rhPSMA-7.3 injection in visualising tumours in subjects with biopsy-proven PCa.
3. To perform kinetic modelling on the distribution of  $^{18}\text{F}$ -rhPSMA-7.3 in subjects with PCa.
4. To use the kinetic modelling data to optimise the imaging protocol for future studies in subjects with PCa.
5. To determine the *in vivo* stability of  $^{18}\text{F}$ -rhPSMA-7.3 injection by determining proportion of radioactive parent compound present over time.

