#### 4.10 Evaluability criteria and additional subjects

Healthy Volunteer Evaluability Criteria:

As it is important that the study has the required number of evaluable healthy volunteers, the following criteria will be applied, and if the healthy volunteer is not evaluable for efficacy, an additional subject may be included in the study to substitute for the non-evaluable subject:

- Completion of scanning sessions I, II and III and collection of venous blood and urine analysis (as described in the Study Imaging Manual) to be able to undertake a calculation of the subject's internal radiation dosimetry.

Patient Evaluability Criteria:

As it is important that each cohort has the required number of evaluable patients, the following criteria will be applied and if the patient is not evaluable for efficacy, an additional subject may be included in the study to substitute for the non-evaluable subject:

- Completion of scanning sessions I and II and collection of venous blood and urine analysis (as described in the Study Imaging Manual) to be able to perform kinetic modelling.
- At least one positive lesion on the F-rhPSMA-7.3 scan.
- Cohort A only: Radical prostatectomy performed within 30 days of the F-rhPSMA-7.3 scan. In case of a delay of the planned surgery by up to 2 days beyond this 30-day window, a subject may still be considered evaluable.

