#### 8.2.4 General statistical considerations

The study is explorative in nature. An analysis of the percent of radioactive parent compound present in blood over time will be performed. Other endpoints will be presented using descriptive statistics.

In general, all data collected will be presented with summary statistics and given in subject data listings. Summary statistics will include at least number of subjects, mean, standard deviation, median, minimum and maximum for continuous data, and frequency and percentage for categorical data. Tables with summary statistics will be divided by group and visit where applicable. Subject data listings will be sorted by treatment, subject and timing of assessments.

For PK assessments, geometric means and CVs will also be presented, where appropriate.

Details of the planned histopathological analysis and the PSMA immunochemistry procedure are given in a separate Histopathology and Immunohistochemistry Manual prepared for this study. The detailed results of such analysis will not be entered into the eCRF, and will be reported separately for each Cohort A subject in a Histopathology and Immunohistochemistry Report to be prepared by the study pathologist and to be included as an Appendix in the Clinical Study Report. The histopathology and immunohistochemistry analysis results that are to be entered into the eCRF are detailed below in section 8.2.6.

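### Section 8.2.3 applies the positive-lesion criterion to the plasma parent-fraction endpoint, which does not depend on a visible lesion (minor)

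*Protocol*

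**What the plan says.** Protocol section 8.2.3 defines two sets, the safety set and the EAS, and assigns everything other than safety to the EAS: "Statistical analyses for the primary and secondary endpoints (besides safety) will be performed using EAS". No exception is made for any secondary endpoint, and no pharmacokinetic set is defined. Besides eligibility and dosing, the EAS requires that a subject "underwent PET/CT scans and met the scan evaluability criteria set out in section 4.10".

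For patients, section 4.10 lists completed scanning sessions with blood and urine collection, a positive lesion on the study scan and, in Cohort A, prostatectomy within a stated window. It presents the list as evaluability for efficacy: "if the patient is not evaluable for efficacy, an additional subject may be included in the study to substitute for the non-evaluable subject". Section 8.1 repeats the lesion condition: "A patient is considered evaluable if at least one positive lesion on the" study scan is seen.

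Two secondary endpoints in section 2.4 matter here:

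- Endpoint 5: "Analysis of % of radioactive parent compound present in plasma over time in healthy volunteers and subjects with PCa". It serves objective 5 in section 2.2, the in vivo stability of the tracer, to be assessed "by determining proportion of radioactive parent compound present over time".
- Endpoint 2: uptake "visualised by PET imaging compared to histopathology in subjects with PCa, if histopathology information is available".

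**The concern.** The synopsis lists parent fraction under pharmacokinetics, apart from the efficacy variables, and section 7.4.4 lists it among the pharmacokinetic parameters. Section 7.4.1 takes the samples from peripheral venous blood. How much of the plasma radioactivity is intact tracer can be measured whether or not a lesion is seen, so an efficacy criterion is being used to select patients for a measure to which it has no stated relevance. The same wording would remove a Cohort A patient's plasma profile if his surgery fell outside the window.

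Scan-negative patients are foreseeable. Section 4.5 admits patients to Cohort B on biochemical recurrence and to Cohort C on biochemical progression, in each case as an alternative to disease shown on imaging. In Cohort A a negative scan is less likely, since the synopsis says that PSMA is overexpressed in nearly all prostate cancers. At stake is precision in very small cohorts, for data that have already been collected.

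Endpoint 2 raises a lesser issue. A patient with histopathology and a negative scan drops out of its tables, so a reader of those tables would not see the patient in whom the tracer showed nothing.

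**Working it through.** The protocol gives no precision or power figure to reproduce. Its headcount adds up: 6 volunteers + 3 × 3 patients = 15.

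**Tracing the rule.** Endpoint 5 is a non-safety secondary endpoint, so 8.2.3 places it in the EAS. The EAS requires the 4.10 criteria, and for patients these require a positive lesion. A scan-negative patient is therefore outside the endpoint 5 analysis. Volunteers have no lesion criterion and are unaffected.

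**Data removed per excluded patient.** Section 7.4.1 gives parent/metabolite samples at 5, 10, 20, 30, 40 and 50 min, which is 6 time points.

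- Cohort of three, no substitute: 6 of 3 × 6 = 18, or 33 %.
- Same cohort with one substitute: 6 of 4 × 6 = 24 collected, or 25 %.
- Nine patients pooled, no substitute: 6 of 9 × 6 = 54, or 11 %.
- Pooled with one substitute: 6 of 10 × 6 = 60, or 10 %.

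**Precision.** The six samples from one patient are not independent, so the patient is the unit. At a given time point SE = SD/√n. At equal SD, the ratio of the SE with the exclusion to the SE with everyone is √(n with everyone / n analysed).

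| Situation | Analysed | Available | SE factor |
|---|---|---|---|
| Cohort, no substitute | 2 | 3 | √(3/2) = 1.22 |
| Cohort, one substitute | 3 | 4 | √(4/3) = 1.15 |
| Pooled, no substitute | 8 | 9 | √(9/8) = 1.06 |
| Pooled, one substitute | 9 | 10 | √(10/9) = 1.05 |

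Section 8.2.4 divides tables by group, so the cohort rows apply to tables by cohort. The pooled rows apply if stability is summarised over all patients.

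**How often it could happen.** The protocol gives no positivity rate for this tracer. Let p be an assumed chance, common to all cohorts, that a patient's scan is positive. The chance of at least one scan-negative patient among the first three of a cohort is 1 − p³. The expected number of scan-negative patients by the time nine positive ones are reached is 9/p − 9.

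| Assumed p | 1 − p³ | 9/p − 9 |
|---|---|---|
| 0.70 | 0.66 | 3.86 |
| 0.80 | 0.49 | 2.25 |
| 0.90 | 0.27 | 1.00 |
| 0.95 | 0.14 | 0.47 |

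These rows are illustrative only.

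**Endpoint 2.** Sections 7.2.3 and 8.2.6 compare SUV in detected lesions with pathology. A scan-negative patient has no detected lesion and so adds no SUV to that comparison in any analysis set. The rule changes only which patients appear: with one scan-negative and three scan-positive Cohort A patients, the endpoint 2 tables show three patients rather than four.

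**The case against.** The strongest reply is that little is lost. Section 8.2.4 says that, in general, everything collected is summarised and listed, so a scan-negative patient's parent fractions should remain visible. That stands, and a reader who infers that the data are thrown away goes further than the text. But a general sentence does not override the specific assignment in 8.2.3, so exclusion from the endpoint analysis remains.

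The pooled loss is also small, at 1.06 or 1.05, and the study is exploratory with no hypotheses. Section 8.2.4 does set this variable apart ("An analysis of the percent of radioactive parent compound present in blood over time will be performed", with other endpoints described), but it states no model or precision target. Section 7.2.2 relates lesion uptake to parent tracer in plasma, so one common set has some rationale. It has that rationale for the kinetic analysis, not for a summary of stability.

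The term scan evaluability in 8.2.3 might be taken to mean scan completion only. Section 8.1 answers this by tying evaluability to a positive lesion. Nor is the matter merely left to the SAP: 8.2.3 has already fixed the set, and a SAP using another would depart from the protocol.

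On endpoint 2, a reader might infer an inflated detection rate or sensitivity. The protocol plans neither. Section 4.10 does not require the positive lesion to lie in the prostate, and histology lesions missed by PET can still appear within an analysed patient. Section 8.2.4 also puts each Cohort A patient's pathology in a report appended to the study report. The objection therefore holds against any claim that a planned estimate is wrong.

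**Conclusion.** The concern holds as a minor point. Section 8.2.3 extends an efficacy criterion to endpoint 5 and so leaves valid plasma profiles out of its analysis. One scan-negative patient raises the standard error by a factor of 1.22 in a cohort of three or 1.06 for nine pooled patients without substitution, and by 1.15 or 1.05 with it. These factors assume equal SD and one excluded patient; the pooled ones also assume that the cohorts can be combined.

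A reader might go on to infer that the parent-fraction estimate is biased. The documents do not support this: nothing in them links scan result to tracer stability, and the loss is one of precision.

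For endpoint 2, the patients analysed are all PET-positive at patient level by construction, which affects presentation and not the planned SUV comparison. Safety, volunteer dosimetry and lesion kinetics (endpoints 3 and 4) are unaffected. The blood and urine radioactivity summaries for patients in section 8.2.9 are not clearly assigned to the EAS and are not part of this conclusion.

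**What to change.** Reword section 8.2.3 to name the set by endpoint:

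1. Endpoint 5: all dosed subjects who meet the eligibility criteria and have usable plasma samples, without the positive-lesion condition and, for Cohort A, without the prostatectomy-timing condition.
2. Endpoint 2: keep the eligibility condition and the present scope, which is any subject with PCa for whom histopathology is available and not Cohort A alone. Show scan-negative patients as such beside their pathology. No detection-rate endpoint needs to be added.
3. Keep the positive-lesion condition for lesion SUV, kinetic modelling and the substitution rule.
4. Report the number of scan-negative and of substituted patients in each cohort.

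The cost is a short rewording and a few table rows, with no new data collection. The drawback is that the number of subjects will differ between endpoints and must be shown in each table.
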